## **13 Safety reporting for WP1 Cohorts 1 and 2**

All safety aspects of the trial will be documented in the ADVANCE Safety Management Plan [34].

The Principal Investigator is responsible for ensuring that all site staff involved in this trial are familiar with the content of this section.

The investigational IVD (OLO (System) is non-invasive and OLO (System) results will not be used to manage participants. Therefore, there is no risk of adverse events associated with the OLO System and reporting of such events is not required.

The investigational medical device (Lancet) used to collect trial-specific finger prick blood samples is invasive and there is a low risk that WP1 participants may experience an Adverse Event (AE). Therefore, Serious Adverse Event (SAE) reporting is required.

All SAEs must be reported immediately (and within 24 hours of knowledge of the event) by the PI at the participating site to the CTR PV and safety specialist unless the SAE is specified as not requiring immediate reporting (see section 13.2).

### 13.1 Definitions

**Table 5.** SAE terminology definitions

Term	Definition
Adverse Event (AE)	Any untoward medical occurrence in a participant or clinical trial participant administered a medical device and which are not necessarily caused by or related to that product
Serious Adverse Event (SAE)	Any adverse event (SAE) that - 
 
• Results in death
 
• Is life-threatening*
 
• Required hospitalisation or prolongation of existing hospitalisation**
 
• Results in persistent or significant disability or incapacity
 
• Consists of a congenital anomaly or birth defect
 
• Other medically important condition***
 

Unexpected Serious Adverse Effect (USAE)	A serious adverse event (SAE) which by its nature, incidence, severity or outcome has not been identified in the protocol or risk assessment and is previously undocumented.

**\*Note:** The term 'life-threatening' in the definition of serious refers to an event in which the trial participant was at risk of death at the time of the event or it is suspected that used or continued used of the product would result in the subjects death; it does not refer to an event which hypothetically might have caused death if it were more severe.

**\*\* Note:** Hospitalisation is defined as an inpatient admission, regardless of the length of stay, even if the hospitalisation is a precautionary measure for continued observation. Pre-planned hospitalisation e.g. for pre-existing conditions which have not worsened, or elective procedures, does not constitute an SAE.

**\*\*\* Note:** other events that may not result in death, are not life-threatening, or do not require hospitalisation, may be considered as an SAE when, based upon appropriate medical judgement, the event may jeopardise the participant and may require medical or surgical intervention to prevent one of the outcomes listed above.

## 13.2 Trial Specific SAE Reporting requirements

In addition to the SAE reporting requirements above, for the purposes of this trial the following events will be considered SAEs and must be captured on the SAE form and reported to the CTR with 24 hours of knowledge of the event:

- Puncture wound, infection, inflammation, or swelling at the site of the lancet finger prick  
Grade ≤2

For the purposes of this trial the following events will **not** require reporting:

- Hospitalisation for neutropenic sepsis
- Death due to neutropenic sepsis
- Any abnormal laboratory measurement associated with the routine or investigational test used to diagnose neutropenic sepsis

**These should be completed in the participant's notes and on the relevant toxicities CRF page and forwarded to the CTR in the normal timeframes for CRFs.**

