Comparator study duration	WP1 Cohorts 1 and 2: 4 months from registration of first patient to end of patient follow-up inclusive of follow-up WP2 and 3: 1 month from issue of Participant Information Sheet (PIS)/Informed Consent Form (ICF) to date of group interview
Comparator study follow-up duration	WP1: 2-4 weeks following registration
Planned trial period	12 months
Primary objective	To clinically evaluate the investigational device (OLO System) versus the comparator standard laboratory device for the management of chemotherapy-related suspected neutropenic sepsis and pre-chemotherapy borderline neutropenia.
Secondary objectives	
 
1) To assess the feasibility of recruiting patients and use of the OLO System;
 
2) To assess the safety of the OLO System in association with the UKONS Oncology/Heamatology 24 hour guidance and triage screening tool (Appendix 1) for patients who telephone for medical advice with suspected neutropenia and sepsis, to maximize both patient safety and independence;
 
3) To assess patient and staff acceptability for the investigative device;
 
4) To assess costs, including issues around hospital care/treatment and admissions.
 
5) To assess which chemotherapy regimens are most likely to be associated with neutropenic sepsis and what current treatment management is;
 
6) Through communication with key stakeholders and Welsh Government, explore the framework required to adequately inform the potential integration of the investigational device and triage questions into routine practice, within Wales and beyond;
 
7) To design a larger UK-wide trial, in collaboration with patient representatives, to formally assess the investigational device for routine use within the NHS.
 

Primary outcomes	Clinical evaluation of the OLO System: Neutrophil count from OLO (System and standard laboratory test full blood count (FBC).

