#### **13.4 Expectedness**

The Chief Investigator (or another delegated appropriately qualified individual) will assess each SAE to perform the assessment of expectedness.

SAEs which add significant information on specificity or severity of a known, already documented ADE constitute unexpected events, i.e. an unexpected serious adverse device event (USAE). For example, an event more specific or more severe than that described in the protocol is considered unexpected.

**Table 5.** Table of expected events for the intervention

Event
Puncture wound, infection, inflammation, or swelling at the site of the (study finger prick Grade $\geq 2$

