**SAE [contact]**  
**(for emergency use only when email is not available)**

SAEs should be reported from time of signature of the WP1 ICF, throughout the follow-up period up to, and including 28 days after the date upon which the WP1 lancet was used on the participant.

A SAE form is not considered as complete unless the following details are provided:

- Full participant trial number
- A SAE
- A completed assessment of the seriousness, and causality as performed by the PI (or another appropriately medically qualified doctor registered on the delegation log).

If any of these details are missing, the site will be contacted, and the information must be provided by the site to the CTR within 24 hours.

All other ADEs should be reported on the CRF following the CRF procedure described in Section 16.

**13.5.2 ..... The CTR responsibilities**

Following the initial report, all SAEs should be followed up to resolution wherever possible, and further information may be requested by the CTR. Follow up information must be provided on a new SAE form.

The CTR should continue reporting SAEs to the REC until 28 days after the participant receives the last part of the intervention, (i.e. from date of finger prick).

Once a SAE is received at the CTR, it will be evaluated by staff at the CTR and sent to the Chief Investigator (or their delegate) for an assessment of expectedness.

For all non-CTIMP studies, including clinical investigations of medical devices, only reports of related and unexpected Serious Adverse Events (SAEs) should be submitted to the REC. These should be sent within 15 days of the chief investigator becoming aware of the event.

There is no requirement for annual safety reports to REC in addition to the information provided through the annual progress report.

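### Lancet-site events are 24-hour SAEs at Grade ≤2 but expected at Grade ≥2 with no upper limit, so reporting can fall as severity rises

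*Protocol*

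**What the plan says.** Section 13.2 opens its trial-specific list with "In addition to the SAE reporting requirements above, for the purposes of this trial the following events will be considered SAEs". The only entry is "Puncture wound, infection, inflammation, or swelling at the site of the lancet finger prick", at Grade ≤2, and such an event "must be captured on the SAE form and reported to the CTR with 24 hours of knowledge of the event".

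Section 13.4 has a one-row table of expected events for the intervention: "Puncture wound, infection, inflammation, or swelling at the site of the (study finger prick Grade", followed by ≥2. It gives no upper grade. The same section says that an event more severe or more specific than the protocol describes counts as unexpected. Section 13.1 defines an unexpected serious effect as one not already identified in the protocol or the risk assessment.

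Section 13.5.2 asks the Chief Investigator or a delegate to judge the expectedness of each SAE, and states that "only reports of related and unexpected Serious Adverse Events (SAEs) should be submitted to the REC". Section 13.5.1 routes other device events to the ordinary CRF.

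On timing, section 13.5.1 runs SAE reporting from consent to "28 days after the date upon which the WP1 lancet was used on the participant". Section 18 instead counts 28 days from collection of the study blood sample, for all participants. Section 12.1.2 allows that sample to be an aliquot of the routine venous tube in place of a finger prick. Table 2 places the follow-up SAE assessment at day 14 to 28, in line with the synopsis ("WP1: 2-4 weeks following registration").

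**The concern.** The same event carries two grade limits pointing in opposite directions. One decides whether it is an expedited SAE; the other decides whether it is expected, which in turn decides whether the REC hears of it. Expedited reporting should not become lighter as an event becomes more severe, and here it can.

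This matters because section 13 gives the lancet as the reason for SAE reporting in the trial (events from the analyser itself are declared not reportable), and section 13.3 assesses causality for the lancet only. The participants have suspected neutropenic sepsis, borderline neutropenia or palbociclib therapy, so an infection at a puncture site is not a remote idea. Section 13.2 also exempts admission for, and death from, neutropenic sepsis from SAE reporting, which leaves somewhat less of a backstop behind this line.

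**Working it through.** No sample size, power or event count is involved, so the check is a trace through the text. I take a higher grade to mean a more severe event.

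**1. The two ranges.** Section 13.2 covers Grade ≤2. Section 13.4 covers Grade ≥2. They share Grade 2 only. Grade 1 is in 13.2 alone, and Grade 3 and above is in 13.4 alone.

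**2. Each grade through 13.1, 13.2, 13.4 and 13.5.**

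| Grade | Trial-specific SAE (13.2)? | In expected-events table (13.4)? | Report to CTR | Report to REC if related |
|---|---|---|---|---|
| 1 | Yes | No | 24 hours | Unclear |
| 2 | Yes | Yes | 24 hours | No |
| 3+, no general criterion met | No | Yes | CRF only | No |
| 3+, a general criterion met | No, but an SAE under 13.1 | Yes | 24 hours | No |

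**3. Why Grade 1 is unclear.** If the table in 13.4 alone decides, a related Grade 1 event is unlisted, hence unexpected, and goes to the REC. But it is less severe than the listed event, and section 13.2 itself names it. Under the wording of 13.1 and 13.4 it therefore need not be unexpected. The protocol does not settle which reading governs.

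**4. Why the severity safeguard does not rescue Grade 3+.** Section 13.4 makes an event unexpected when it is more severe than described. The description is Grade ≥2 without a ceiling, so no grade exceeds it. The safeguard can still work on specificity, but not on grade.

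**5. Could one sign be a slip or a conversion error?** Each sign is rendered explicitly in its own section, but the possibility cannot be excluded, so I tried reversing each in turn.
- If 13.2 were ≥2 and 13.4 stayed as it is, every event on the 13.2 list would be expected, and on grade none would reach the REC.
- If 13.4 were ≤2 and 13.2 stayed as it is, a Grade 3+ event meeting no general criterion would still miss the 24-hour route that Grade 1 triggers.

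Reversing a single sign does not remove the need to reconcile the sections.

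**6. The linked timing rules.** For a participant who gives only a venous aliquot, the date of lancet use in 13.5.1 does not exist; the sample date in section 18 does. The scheduled SAE assessment may take place at day 14 and the window closes at day 28, so it can precede closure by up to 28 − 14 = 14 days.

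**The case against.** The best defence is that other rules do much of the work, and much of it stands.

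- A reader might infer that trivial punctures flood the REC, perhaps one for each of the 72 planned participants plus re-takes. The documents do not support that. Section 13.2 sends these events to the CTR; the REC sees only those judged related and unexpected, and for Grade 1 that judgement is open. An adverse event under 13.1 must be untoward, which the intended puncture arguably is not. Participants may also give a venous aliquot, so 72 finger pricks is not a planned number. What remains is that 13.2 names a puncture wound, sets no lower limit and does not exclude the intended one.
- A reader might infer that severe events are suppressed. That goes too far. The 13.2 list adds to the general criteria, which include a category for other medically important conditions, so a serious Grade 3+ event still reaches the CTR within 24 hours. Other device events go on the CRF, and the management group and the Executive Committee review safety. What survives is narrower: no REC report for the serious event, and no 24-hour report for the non-serious one.
- Nor is this line the trial's whole device-safety signal. The general SAE criteria, the CRF route, and the site and manufacturer reporting in section 13.6, which covers the lancet, all operate without it.
- A reader might infer that half of the 28-day window goes unobserved when follow-up is at day 14. Sections 13.5.1 and 18 make SAE reporting a continuing duty to day 28, so those days lack only a scheduled check.
- The missing lancet date is largely answered by section 18, and no lancet-related event can be missed where no lancet was used. It is a mismatch of wording.

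**Conclusion.** The contradiction between sections 13.2 and 13.4 is real and holds on the text. Read with 13.5.2, it gives a wrong reporting result for Grade 3 and above: CRF only if no general seriousness criterion is met, and CTR but not REC if one is. It leaves the REC status of a related Grade 1 event undetermined. The timing mismatches are genuine but minor.

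The size is qualitative. The protocol gives no expected number of lancet-site events by grade, so no count of misrouted reports can be derived. Nothing here touches the primary outcome, any estimate or the sample size. The conclusion assumes that the two signs are as printed and that the open-ended entry in 13.4 is applied literally when expectedness is judged. The documents do not show which threshold was intended.

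**What to change.** Ask the sponsor's safety lead to:

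1. Reconcile the grade thresholds in sections 13.2 and 13.4. This review proposes no threshold.
2. Check the reconciled text against the REC rule in 13.5.2, grade by grade as in the table above, so that reporting does not fall as severity rises and every grade has one clear route.
3. State whether the intended lancet puncture counts as an event.
4. Use one anchor for the 28-day SAE window in sections 13.5.1, 13.5.2 and 18. It must exist for participants who give only a venous aliquot; the study sample date already used in section 18 does.
5. Add a records-based SAE check at or after day 28, so that the scheduled assessment aligns with the close of the window.

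The cost is protocol and SAE-form wording, and a slightly later record check for some participants.

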## 13.3 Causality

Causal relationship will be assessed for the intervention:

Device intervention: HTL-Strefa S.A. Prolance Max Flow Lancet or similar
---------------------------------------------------------------------------------

The Principal Investigator (or another delegated medically qualified doctor from the trial team) will assess each SAE to determine the causal relationship and the CI (or another appropriately qualified member of the TMG) can also provide this assessment where necessary:

Relationship	Description	Reasonable possibility that the SAE may have been caused by the intervention?
Unrelated	There is no evidence of any causal relationship with the intervention	No
Unlikely	There is little evidence to suggest there is a causal relationship with the intervention (e.g. the event did not occur within a reasonable time after administration of the trial medication). There is another reasonable explanation for the event (e.g. the participant's clinical condition, other concomitant treatment).	No
Possible	There is some evidence to suggest a causal relationship with the intervention (e.g. because the event occurs within a reasonable time after administration of the trial medication). However, the influence of other factors may have contributed to the event (e.g. the participant's clinical condition, other concomitant treatments).	Yes
Probable	There is evidence to suggest a causal relationship and the influence of other factors is unlikely.	Yes
Definite	There is clear evidence to suggest a causal relationship and other possible contributing factors can be ruled out.	Yes

The causality assessment given by the Principal Investigator (or delegate) cannot be downgraded by the Chief Investigator (or delegate), and in the case of disagreement both opinions will be provided.

#### **13.4 Expectedness**

The Chief Investigator (or another delegated appropriately qualified individual) will assess each SAE to perform the assessment of expectedness.

SAEs which add significant information on specificity or severity of a known, already documented ADE constitute unexpected events, i.e. an unexpected serious adverse device event (USAE). For example, an event more specific or more severe than that described in the protocol is considered unexpected.

**Table 5.** Table of expected events for the intervention

Event
Puncture wound, infection, inflammation, or swelling at the site of the (study finger prick Grade $\geq 2$

### **13.5 Reporting procedures**

#### **13.5.1 ..... Participating Site Responsibilities**

The PI (or delegated appropriately qualified doctor from the trial team) should complete a copy of the ADVANCE SAE Case Report Form (CRF) [35] and sign and date the CRF to acknowledge that he/she has performed the seriousness and causality assessments. Investigators should also report SAEs to their own health boards or trust in accordance with local practice.

The completed CRF for all events requiring immediate reporting should be submitted via email to the CTR within 24 hours of knowledge of the event. A separate form must be used to report each event, irrespective of whether or not the events had the same date of onset.

The participant will be identified only by ADVANCE Participant Trial Number and age at time of SAE. The participant's name should not be used on any correspondence.

It is also required that sites respond to and clarify any queries raised on any reported SAEs and report any additional information as and when it becomes available through to the resolution of the event. Additionally, the CTR may request additional information relating to any SAEs and the site should provide as much information as is available to them in order to resolve these queries.

**SAE [contact]**  
**(for emergency use only when email is not available)**

SAEs should be reported from time of signature of the WP1 ICF, throughout the follow-up period up to, and including 28 days after the date upon which the WP1 lancet was used on the participant.

A SAE form is not considered as complete unless the following details are provided:

- Full participant trial number
- A SAE
- A completed assessment of the seriousness, and causality as performed by the PI (or another appropriately medically qualified doctor registered on the delegation log).

If any of these details are missing, the site will be contacted, and the information must be provided by the site to the CTR within 24 hours.

All other ADEs should be reported on the CRF following the CRF procedure described in Section 16.

**13.5.2 ..... The CTR responsibilities**

Following the initial report, all SAEs should be followed up to resolution wherever possible, and further information may be requested by the CTR. Follow up information must be provided on a new SAE form.

The CTR should continue reporting SAEs to the REC until 28 days after the participant receives the last part of the intervention, (i.e. from date of finger prick).

Once a SAE is received at the CTR, it will be evaluated by staff at the CTR and sent to the Chief Investigator (or their delegate) for an assessment of expectedness.

For all non-CTIMP studies, including clinical investigations of medical devices, only reports of related and unexpected Serious Adverse Events (SAEs) should be submitted to the REC. These should be sent within 15 days of the chief investigator becoming aware of the event.

There is no requirement for annual safety reports to REC in addition to the information provided through the annual progress report.

### **13.6 IVD and medical device defect and deficiency reporting**

Sites will be responsible for reporting suspected problems or incidents with the CE marked investigational devices (e.g. OLO (System and components, or Lancet) directly to the MHRA via the MHRA Yellow Card Scheme following local and MHRA procedures.

The device manufacturers (OLO (and lancet manufacturer) will be responsible for reporting defects and deficiencies of the devices directly to the MHRA via the MHRA Manufacturer’s On-line Reporting Environment (MORE) national reporting system following manufacturer and MHRA procedures.

### **13.7 Contraception and pregnancy**

#### **13.7.1 ..... Contraception**

There is no requirement for women of childbearing potential entering into this trial, or male participants with such a partner to use a contraceptive during of following participation in the trial.

#### **13.7.2 ..... Pregnancy reporting whilst participating in the trial**

Pregnancy, or the pregnancy of a partner occurring whilst participating in the trial, or a congenital anomaly or birth defect associated with the intervention device, is highly unlikely and not considered an SAE. Therefore, this trial will not require pregnancy reporting or follow-up.

### **13.8 Urgent Safety Measures (USMs)**

An urgent safety measure is an action that the Sponsor, Chief Investigator or Principal Investigator may carry out in order to protect the subjects of a trial against any immediate hazard to their health or safety. Any urgent safety measure relating to this trial must be notified to the REC immediately by telephone, and in any event within 3 days in writing, that such a measure has been taken. USMs reported to the CTR will be handled according to CTR USM reporting processes.

## **14 Statistical considerations**

### **14.1 Sample size**

#### **14.1.1 WP1 Device cohort study**

##### **Cohorts 1 and 2 combined:**

We will evaluate the concordance between the OLO neutrophil result and the standard of care laboratory result from the same time period, across all patients with a valid output. A valid OLO neutrophil result will be one which produces a test result which is within  $\pm 0.2 \times 10^9/L$  of the standard laboratory result.

